An Adverse Events questionnaire will be used to record study side-effects. This questionnaire will capture the date, visit number, adverse event description, event start date, event end date, relationship to the device, severity, whether it is a SAE (Serious Adverse Event), action taken and outcome, The PI and/or, Medical Monitor and clinical co-investigators will make decisions regarding the severity of the side-effects, the relationship to the device and whether or not it a SAE.

Early stopping rules:

Subjects will be removed from the study early if it becomes clear that the risks of continuing treatment outweigh the benefits of continuing the study. In this research study, there is no alternative treatment other than treatment with LFR rTMS vs sham. If subjects are unable to complete the study, they will be either be absorbed in the PI's Brain Injury clinic or referred to appropriate treatment centers, if they so desire.

The following will be used to define unacceptable tolerability:

This decision will be made by a review committee chaired by the Medical Monitor.

- (a) Clinically judged treatment-related death in one research participant. Clinically judged medication related death in one research participant. If a death occurs the case will be reviewed to decide if the death was medication related. The review committee will include [name] (PI), and members of the Data & Safety monitoring board: [name], [name] and [name]. All members of the DSM board are psychiatrists and faculty Johns Hopkins University. The 3 DSM members are not connected with the study.

[name] will also serve as the medical monitor. He is currently involved in several clinical trials and therefore, is well-suited for this role. As the medical monitor, his job will be to: (a) review and provide appropriate recommendations to address unanticipated problems that may arise during the study, and

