(b) if anything adverse happens during the study period, he will provide an unbiased written report to the Johns Hopkins IRB and Department of Defense Human Research Protection Office (DoD HRPO) within 10 days of the event. He will not work under the supervision of the PI or any other research staff but will be available to the PI and research team to address any issues that arise during the study period. He will have the authority to stop the study, remove subjects from the study and take whatever steps are necessary to protect the safety and well-being of research volunteers until the IRB can assess the medical monitors report.

(a) Clinically judged treatment related hospitalization and/or emergency room visit in 20 % or more participants.

(b) Drop out of the study secondary to intolerable side-effects in 30% or more of participants
If any of the above happens, the study will be immediately terminated.

If either of the above happens, the study will be immediately terminated.

Otherwise, the Adverse-Events Protocol will be used to track the nature, visit time, and severity of side-effects

The PI and her research team will meet regularly to discuss the progress of the study.

In summary, all unanticipated problems involving risk to subjects or others related to participation in the study will be promptly reported both to Hopkins IRB and to the USAMRMC, Office of Research Protections, Human Research Protection Office (<[contact]>; email - [contact] or by [contact]).

A complete written report will follow the initial notification. In addition to the methods above, the complete report will also be sent to the U.S. Army Medical Research and Materiel Command, ATTN: MCMR-ZB-PH, [name].”

7. Risks & Benefit

As with any medical treatment, rTMS carries a risk of side effects. However, rTMS is generally well-tolerated and only a small percentage of patients discontinue treatment because of side effects which are even less frequent with LFR than with HFL rTMS.

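### The 20% and 30% stopping limits name neither arm nor denominator; pooled with sham, they need about twice those rates in the active arm if all harm falls there

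*Combined protocol and SAP*

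**What the plan says.** Section 6 (Study Statistics), under Early stopping rules, gives three grounds for terminating the study. The first is "Clinically judged treatment-related death in one research participant". The other two are percentages: "Clinically judged treatment related hospitalization and/or emergency room visit in 20 % or more participants", and "Drop out of the study secondary to intolerable side-effects in 30% or more of participants". Neither percentage is tied to an arm, and neither is said to apply to the planned number or to those enrolled so far.

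On who decides, the same section states: "This decision will be made by a review committee chaired by the Medical Monitor". The committee includes the PI and three data and safety monitoring (DSM) members who have no connection with the study. Of the medical monitor it says "He will have the authority to stop the study, remove subjects from the study and take whatever steps are necessary", and that after an adverse happening "he will provide an unbiased written report to the Johns Hopkins IRB and Department of Defense Human Research Protection Office" within 10 days.

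The Abstract (Study Design) plans 15 active and 15 sham participants. Section 4 describes a sham coil with almost no field plus simulated scalp sensation, and a research team that is blind apart from one rTMS staff member. No section provides safety counts by arm to the monitor or the committee.

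**The concern.** A limit on all participants mixes those exposed to the stimulation with those who are not. Under 1:1 allocation, if sham contributes no events, the active-arm rate must be about double the written percentage before the limit is met. For example, 5 of 15 active participants (33%) could be hospitalised or seen in an ER because of treatment, with none on sham. That is 5 of 30 (17%), short of a 20% limit read on the planned 30.

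This matters because section 5 says that the safety and tolerability of rTMS are untested in depression after TBI, and section 4 allows that this population may carry a higher seizure risk. The written limits should be able to respond to an excess among the people actually stimulated.

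**Working it through.** **Denominator.** The plan gives no event counts for its limits, so the figure to reproduce is the sample size. Table 7 (power 0.9, remission 0.7 against 0.1, two-sided alpha 0.05) gives 15 per arm. The two-proportion formula gives (1.960 × √(2 × 0.4 × 0.6) + 1.282 × √(0.7 × 0.3 + 0.1 × 0.9))² / 0.6² = 11.8. With the continuity correction this becomes 14.9, so 15 per arm and 30 in total. Table 7 reproduces.

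**Counts needed on the planned 30.** These are participants, not events.
- Hospitalisation or ER: 0.20 × 30 = 6. If all are active, 6/15 = 40%.
- Side-effect dropout: 0.30 × 30 = 9. If all are active, 9/15 = 60%.
- The same percentages of 15 active participants are 3 (0.20 × 15) and 5 (0.30 × 15 = 4.5, rounded up).

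**Chance of reaching each count.** The documents give no rates for these events, so all true rates below are assumptions. Two readings of the denominator are shown.
- Planned 30: active and sham counts are independent binomials on 15 each. With no sham events and a true active rate of 20%, P(X ≥ 6) = 1 − P(X ≤ 5) = 1 − 0.939 = 0.061.
- Running percentage: participants enter in random order, 15 per arm. The percentage is checked after each one from the 10th onward, which is a further assumption (2 and 3 of the first 10 meet the limits).
- Active-arm count: P(X ≥ 3) = 1 − P(X ≤ 2) = 1 − 0.398 = 0.602 at a true 20%.

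With no sham events:

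| Limit | True active rate | Pooled, planned 30 | Pooled, running | Active-arm count |
|---|---|---|---|---|
| Hospitalisation/ER | 20% | 0.06 | 0.32 | 0.60 (3 of 15) |
| Hospitalisation/ER | 30% | 0.28 | 0.60 | 0.87 (3 of 15) |
| Dropout | 30% | 0.02 | 0.21 | 0.48 (5 of 15) |
| Dropout | 40% | 0.10 | 0.41 | 0.78 (5 of 15) |

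**Sham events.** These can occur, since relatedness is judged mostly blind and sham participants feel simulated sensation. In the row order of the table, the planned-30 figures are 0.16, 0.43, 0.05 and 0.20 at a 5% sham rate, and 0.29, 0.58, 0.12 and 0.32 at 10%. Repeating the running calculation with a 10% sham rate gives 0.59, 0.80, 0.41 and 0.63. On that combination the hospitalisation limit is almost as likely to fire at a true 20% as the active-arm count is to be reached (0.59 against 0.60).

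**Needless alarms from the active-arm counts.** P(X ≥ 3 of 15) is 0.04 at a true active rate of 5% and 0.18 at 10%. P(X ≥ 5 of 15) is 0.01 at 10%.

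**The case against.** The strongest reply is that the low figures belong to one reading. A rule that terminates the study immediately can as well be read on participants to date, and then it is far more sensitive. A reader might infer from 0.06 and 0.02 that the limits are nearly blind to active-arm harm. The documents do not support that, because they do not fix the denominator. What survives is a gap under both readings when sham events are absent; it narrows as sham events are added.

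Second, other safeguards act well before six participants are affected. One treatment-related death ends the study, the monitor can stop it on his own authority and reports within 10 days, and section 7 removes participants with a seizure or intolerable effects from treatment. Section 7 also expects that "only a small percentage of patients discontinue treatment because of side effects", so the dropout rates used here are stress cases. A reader might infer that participants are left unprotected; these provisions show otherwise. They do not, however, give anyone counts by arm.

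Third, a reader might infer that 3 of 15 and 5 of 15 active should be mandatory stops. That is a debatable trade. With equal rates in both arms, stopping at 6 of 30 or 3 of 15 active gives false stops of 0.04 at 5% and 0.20 at 10%, against 0.003 and 0.07 for 6 of 30 alone. Run as a rescaled percentage from the 5th active participant, the active-arm rule stops falsely with about 0.25 at 5% and 0.48 at 10%. This objection stands, so the counts should prompt review only.

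Last, by-arm review strains the blind. The PI sits on the committee, and the PI and/or "Medical Monitor and clinical co-investigators will make decisions regarding the severity of the side-effects, the relationship to the device". This can be managed by the order of the steps, but it is a real cost.

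**Conclusion.** The point holds as an optional, cheap safety improvement. The limits name no arm and no denominator, and pooling with sham means that they need about twice the written percentage in the active arm if all harm falls there. With no sham events, the hospitalisation limit fires with 0.06 to 0.32 at a true active rate of 20% and 0.28 to 0.60 at 30%, against 0.60 and 0.87 for the active-arm count. The dropout limit fires with 0.02 to 0.21 at 30% and 0.10 to 0.41 at 40%, against 0.48 and 0.78.

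These sizes rest on assumed event rates, full enrolment of 15 per arm and, for the upper figures, checks starting at the 10th participant. The shortfall is smaller if sham participants also have events judged related. Nothing here touches the efficacy analysis.

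**What to change.** Keep the pooled 20% and 30% limits as the mandatory stops, and say which denominator they use. Then add:
- Relatedness is judged blind first.
- The unblinded rTMS staff member then gives active-arm counts to the medical monitor and the three DSM members only; the blinded PI sits out.
- Three active participants with a hospitalisation or ER visit judged due to treatment, or five with side-effect dropout, prompt an unscheduled review by them, not automatic termination.
- These counts stay fixed and are not rescaled during accrual.

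The cost is a few sentences and a change in how the committee works. The independent reviewers learn the allocation of the few affected participants, and the PI misses that review. A needless review on the hospitalisation count occurs with probability 0.04 at a true active rate of 5% and 0.18 at 10%. Fixed counts are also less sensitive if fewer are treated: 3 of 10 is 30%, and 5 of 10 is 50%.

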Study Design: We propose a double-blind placebo controlled proof of concept pilot study of active versus sham LFR rTMS for the treatment of TBI depression. As noted above, all subjects will be screened prior to randomization. During the screening visit, all subjects will undergo a complete psychiatric evaluation as well as formal cognitive testing. In addition, if there is any possibility of pregnancy or unstable medical status, the PI or physician co-investigator will ask the potential subject's treating psychiatrist or primary care physician (PCP) to conduct a urine pregnancy test and/or bloodwork to rule out infections and liver, kidney or thyroid abnormalities. If the potential participant does not have a PCP or psychiatrist, a lab requisition will be provided to the participant. He/she will be considered for the study only after the lab results are reviewed by the study physician and found to be normal. .

Subjects will be randomized using a custom in-house software method, and will be stratified on time since injury: <5 years post injury versus ≥ 5 years.

All members of the research team will be blind to individual subjects' treatment condition, with the exception of the rTMS staff member, [name]. The success of subject blinding will be evaluated by asking subjects, during the first and last week of treatment, whether they believe that they received active or sham rTMS treatment. The rTMS technician will ask this question and note down the answer in the weekly assessment form.

Study Treatment: Subjects will receive either LFR rTMS or sham treatment.

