rTMS Treatment & Sham Treatment: rTMS will be delivered at the Brain Stimulation Program at The Johns Hopkins Hospital, using a Magstim Super Rapid 2 stimulator with a focal double 70-mm air cooled coil. Control patients will receive treatment using an identically appearing coil that produces the same sound and is the same weight as the active coil, but has negligible magnetic field strength. Scalp sensation in control subjects will be simulated using the sham system described in Borckardt et al⁸⁸. Prior to each treatment, subjects will be instructed to insert earplugs. The head of the seated subject will be secured in a head and coil holder chair and stand assembly (Rogue Research Inc.). Motor threshold (MT) will be ascertained by delivering single pulses to the area of the motor cortex (right side) controlling the contralateral abductor pollicis brevis (APB). Electrical activity in APB will be recorded using surface electrodes. MT will be defined as the lowest intensity of stimulation that produces motor evoked potentials of at least 50 μ V in 5 out of 10 trials. MT will be determined prior to the first treatment and weekly thereafter. The stimulation site for LFR over the DLPFC will be F4 of the International 10-20 System for Electrode Placement. . Treatment will be delivered by a TMS technician, or by co-investigator [name], or by another physician credentialed to deliver TMS at The Johns Hopkins Hospital and approved by the IRB.

To determine optimal TMS treatment parameters we have reviewed the published literature reporting LFR rTMS for the treatment of major depression, and also rely on our own clinical experience using LFR rTMS to treat patients with idiopathic depression. We also take into account that although we are excluding subjects at increased risk for seizure with rTMS, such as those with a history of epilepsy, abnormal EEGs or focal abnormality on brain imaging, our TBI study population may nonetheless be at a higher risk.

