Adult TBI patients will be considered for the study in accordance with the following inclusion and exclusion criteria.

Inclusion criteria:

- a) Adults aged 18 and over
- b) H/o closed head injury
- c) Must meet DoD criteria for mild or moderate TBI
- d) Time duration since injury greater than 3 months
- e) Must meet criteria for major depression as assessed by the Structured Clinical Interview for DSM-IV (SCID) and a score greater than 10 on the HAM-D17

Exclusion criteria:

- a) Subjects with skull fracture
- b) Less than 3 months since injury
- c) Subjects who meet DoD criteria for severe TBI
- d) Subjects who are on psychotropics or mood stabilizing medications (e.g. antidepressants, antipsychotics, anxiolytics, sedative/hypnotics).
- e) Subjects who are medically unstable
- f) History of active substance abuse x 1 month
- g) Current psychotic illness
- h) Evidence of frontal lesions on brain scan (including patients who have undergone surgery for hemorrhage or clot evacuation in the frontal lobe, and patients who have had frontal lobe contusions and or subdural hematoma in the frontal regions)
- i) Individuals with a significant neurological disorder that could increase risk for seizures such as brain tumor, cerebral aneurysm, any h/o seizures and/or family h/o seizures

- j) Dementia
- k) Mini Mental State Exam score of less than or equal to 24
- l) A positive and unmitigated response to any question on the Transcranial Magnetic Stimulation Safety Screen questionnaire
- m) ECT treatment within 6 months prior to the screening visit
- n) History of treatment with rTMS therapy for any disorder
- o) History of treatment with Vagus Nerve Stimulation (VNS)
- p) History of treatment with Deep Brain Stimulation (DBS)
- q) Cardiac pacemakers, implanted medication pumps, intracardiac lines,
- r) Intracranial implant (e.g., aneurysm clips, shunts, stimulators, cochlear implants, or electrodes) or any other metal object within or near the head, excluding the mouth, that cannot be safely removed.
- s) Implanted neurostimulators
- t) Known or suspected pregnancy
- u) Investigators, personnel affiliated with this study, and their immediate families.

5. Drugs/ Substances/ Devices

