During the treatment, the patient may experience tapping, facial twitching, or painful sensations at the treatment site during stimulation. These types of sensations are reported by about one third of patients receiving rTMS. In addition, about half of patients treated with rTMS experience headaches. Both discomfort and headaches tend to get better over time and headaches generally respond very well to over-the counter pain medications. Because the TMS device produces a loud click with each pulse, patients must wear earplugs during treatment to minimize the risk of hearing loss. There have been no reported cases of permanent hearing loss with properly functioning hearing protection.

The most serious known risk of rTMS is the triggering of a seizure. Although there have been a few case reports of seizures with the use of TMS devices, the risk is extremely small and even lower with LFR than with HFL. Moreover, patients with a personal or family history of a seizure disorder or with focal brain pathology will be excluded from the study. Also, the TMS stimulation parameters utilized in this trial fall well within established safety guidelines for the use of TMS that are designed to minimize the risk of seizures with this technique.

As with all antidepressant treatments, there is a small risk for the emergence of mania with rTMS therapy. Also, rTMS therapy is not effective for all patients with depression, and there is a risk that the patient's depression will get worse. Moreover, 50% of subjects in this trial will receive sham stimulation.

There are no known adverse cognitive effects associated with rTMS therapy.

TMS should not be used by anyone who has non-removable magnetic-sensitive metal in their head or within twelve inches of the electromagnetic coil. Objects that may have this kind of metal include: aneurysm clips or coils; stents in your neck or brain; implanted stimulators; cardiac pacemakers or implantable cardioverter defibrillator (ICD); cardiac stents; electrodes for monitoring brain activity; metallic implants in the ears or eyes; shrapnel or bullet fragments; facial tattoos with metallic or magnetic sensitive ink; other metal devices or objects implanted in or near the head. Patients with any such objects will be excluded from the trial.

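### The safety text says focal brain abnormality at any site is excluded to limit seizure risk, but the exclusion criteria name only frontal lesions on brain scan and no EEG finding

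*Combined protocol and SAP*

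**What the plan says.** Two places describe whom the trial keeps out because of seizure risk.

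- Section 7 (Risks & Benefit), on seizure as the most serious known risk: "patients with a personal or family history of a seizure disorder or with focal brain pathology will be excluded from the study". No brain region is specified.
- Section 4, rTMS Treatment & Sham Treatment, on the choice of stimulation parameters: the investigators say they are excluding people at raised seizure risk, "such as those with a history of epilepsy, abnormal EEGs or focal abnormality on brain imaging". Again no region is specified. This is the only place where an abnormal EEG is given as a ground for exclusion.

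The list that decides entry is in Section 4, Inclusion/Exclusion Criteria, which opens: "Adult TBI patients will be considered for the study in accordance with the following inclusion and exclusion criteria". The entries that bear on this point are:

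- (h): "Evidence of frontal lesions on brain scan". One example it gives is "patients who have had frontal lobe contusions and or subdural hematoma in the frontal regions"; the other is earlier surgery in the same lobe for a bleed or clot.
- (i), which deals with conditions that raise seizure risk: "Individuals with a significant neurological disorder that could increase risk for seizures such as brain tumor, cerebral aneurysm". It also covers seizures in the person or the family.
- (l): "A positive and unmitigated response to any question on the Transcranial Magnetic Stimulation Safety Screen questionnaire". The items of that questionnaire are not in the documents.
- (a), (c) and (r): skull fracture, severe TBI, and intracranial implants or metal in or near the head.

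**The concern.** The safety text describes a wider exclusion than the eligibility list applies. Take a person with a closed head injury of mild or moderate severity, a temporal contusion on an old scan, no seizures and no family history of seizures. Section 7 and the treatment section both call this person excluded, yet no listed criterion clearly says so. The case is foreseeable: Section 3 (Pathophysiology of TBI & TBI Depression) names the tips of the temporal lobes, with the frontal regions, as the places where focal injury is most often found.

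The safeguard also supports other text. It appears in the reasoning behind the stimulation parameters, and when Section 7 later reaches the steps taken to reduce risk it only points back to what was said above. A reader assessing the risk would credit an exclusion that screeners are not clearly told to apply, and two screeners could decide the same patient differently. A person who entered in this way and was randomised to active treatment would receive 20 sessions of 1200 pulses, or 20 × 1200 = 24,000 pulses, at 110% of motor threshold.

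**Working it through.** No sample size, power or error rate is involved, so the check is a comparison of texts.

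**Step 1. Match each stated safeguard to the criteria.**

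| Ground for exclusion | Treatment section (Section 4) | Section 7 | Eligibility list |
|---|---|---|---|
| Personal history of seizures or epilepsy | yes | yes | yes, (i) |
| Family history of seizures | no | yes | yes, (i) |
| Focal abnormality, any site | yes | yes | frontal only in (h); tumor and aneurysm in (i) |
| Abnormal EEG | yes | no | not named |

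The seizure-history grounds agree. Focal abnormality is covered in part. Abnormal EEG is not covered by name.

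**Step 2. Count.** Exclusions (a) to (u) make 21. One, (h), refers to a lesion on a brain scan. None mentions EEG.

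**Step 3. Ask whether another criterion reaches a non-frontal traumatic lesion.**

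- (i) is open-ended, because its examples only illustrate. They are tumor, aneurysm and seizure history. Neither a traumatic lesion nor an EEG finding is among them. If (i) were meant to cover every focal traumatic lesion, the frontal criterion (h) would have little left to do.
- (l) might reach such a lesion or an EEG finding. Its questions are not shown, so this cannot be settled either way.
- (a), (c) and (r) remove people with skull fracture, severe TBI or implants. They do not address a temporal contusion in someone with mild or moderate closed head injury.

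**Step 4. Result.** The gap is clearest for non-frontal traumatic lesions, where two passages state a safeguard with no limit of site and the only lesion criterion has one. It is weaker for EEG, where a single passage gives the safeguard as one example.

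**The case against.** The best reply is that the texts can be partly reconciled. The treatment section sits in the same Section 4 as the criteria and says whom the investigators regard as at raised seizure risk. A screener could read the open-ended (i) in that light and turn away someone with a temporal contusion or an abnormal EEG. The questionnaire in (l) may do the same, and Section 3 refers to a fuller safety review in the IRB application that is not among the documents. This stands to the extent that some of these patients may be caught, so confidence is moderate. It does not remove the inconsistency, because exclusion would then depend on how a screener reads (i) or on a form that cannot be seen, while (h) points to a frontal limit.

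It can also be said that a frontal-only criterion is a reasonable choice, since stimulation is at F4 over the right dorsolateral prefrontal cortex and the sample of 30 was chosen for feasibility. That is fair, and it is why narrowing the safety text is an acceptable remedy. It does not justify leaving both texts in place.

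Two stronger readings are tempting. A reader might infer that nobody checks scans or EEGs at screening, because Study Design in Section 4 says only "During the screening visit, all subjects will undergo a complete psychiatric evaluation as well as formal cognitive testing" and then describes conditional pregnancy and blood tests. That list is not exhaustive. It does not name the SCID, the HAM-D, the Mini Mental State Exam or the safety questionnaire either, and all of these are needed for eligibility. Criterion (h) itself presupposes that some scan is consulted. A reader might also infer that participants are told of the wider exclusion and rely on it. The placebo justification promises only a general discussion of risks and benefits, and the consent pages are not available.

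**Conclusion.** The point holds as an inconsistency between the stated safeguard and the listed criteria. Focal brain abnormality is said twice, without limit of site, to be excluded, while the only criterion on scan lesions is frontal in its wording and in every example. Abnormal EEG is said once to be excluded and is named in none of the 21 exclusions. The conclusion assumes that screeners work from the listed criteria, as their opening sentence indicates, and that the unseen questionnaire does not already close the gap. Because the second assumption cannot be checked, confidence is moderate.

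The number of people affected cannot be given: the documents report no rate of non-frontal lesions or abnormal EEGs in this population. A reader might infer that the gap exposes participants to a raised seizure risk. The documents do not show that. The figure in Section 3, one seizure among 1200 stroke patients, concerns a different population, and that seizure followed high-frequency stimulation on the side of the lesion, whereas this trial uses low frequency. It gives no usable rate here.

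The matter should still be corrected, because it concerns a stated protection against the most serious known risk and the correction is cheap.

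**What to change.** Make the texts agree by one of two routes.

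**A. Widen the criteria.** Reword (h) to *evidence of any focal lesion on available brain CT or MRI, including frontal lesions*, keeping the present frontal examples, and add *known abnormal EEG* as an exclusion. Both would be judged from existing reports, with no new scan or EEG. The cost is two changes of wording, the reading of reports already on file, and somewhat narrower recruitment, by an amount the documents do not allow to be estimated. A person with no existing report would remain unchecked.

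**B. Narrow the safety text.** If a frontal-only exclusion is intended, leave the criteria alone. In the treatment section of Section 4 and in Section 7, refer to frontal lesions in place of focal abnormality or focal pathology, and delete abnormal EEGs from the treatment section. Tumor, aneurysm and seizure history stay covered by (i). The cost is wording only, and the seizure argument in Section 7 then rests openly on the narrower exclusion.

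The choice belongs to the sponsor and investigators. Neither route alters dose, sample size, endpoints or analysis.
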